6.4.2. Permitted Drugs

With the exception of the agents described in Section 10.6, any other concomitant medication deemed necessary for the welfare of the subject during the study may be given at the discretion of the investigator. If the permissibility of a specific medication/drug is in question, please contact the Sponsor's designated Medical Monitor. Any medication or vaccine (including over-the-counter or prescription medicines, vitamins, and/or herbal supplements) that the subject is receiving at the time of enrollment or receives during the study must be recorded in the eCRF.

6.5. Dose Modification

No dose modification of study drug is permitted. Study drug should be withheld for liver test abnormalities as described in Section [8.4.6.2](#).

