7.1. Discontinuation of Study Drug

Subjects who discontinue study drug will complete the Week 52/Early Withdrawal assessments specified in the Schedule of Assessments (Section 1.3).

Reasons for discontinuation from the study drug include the following:

- Any AE of urinary retention
- Any occurrence of PVR volume \geq 300 mL

Discontinuation of study drug for abnormal liver function should be considered by the investigator when a subject meets all of the conditions outlined in Section 8.4.6.2 for Hy's law or if the investigator believes that it is in best interest of the subject (reason for discontinuation will be AE).

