 - For subjects with systolic blood pressure < 140 mmHg and diastolic blood pressure < 90 mmHg at the Study URO-901-3005 baseline assessment, the average of 3 systolic blood pressures ≥ 140 mmHg or diastolic blood pressures ≥ 90 mmHg (or both) at any 2 consecutive visits after baseline
 - For subjects with systolic blood pressure ≥ 140 mmHg or diastolic blood pressure ≥ 90 mmHg at Study URO-901-3005 baseline, an increase compared to baseline at 2 consecutive visits in the average of 3 systolic blood pressures by ≥ 20 mmHg or 3 diastolic blood pressures by ≥ 10 mmHg
 - Initiation or increase in dose of medication for treatment of hypertension in any subject
- Adverse events consistent with orthostatic hypotension as confirmed by orthostatic vital signs

- Elevated serum aspartate aminotransferase (AST) or alanine aminotransferase (ALT) lab value requiring that study drug be temporarily withheld or permanently discontinued (see Section 8.4.6.1 and 8.4.6.2). To date, no concern regarding drug-induced liver toxicity has been identified; however, the Sponsor is monitoring laboratory data for a potential safety signal, consistent with Food and Drug Administration guidance [[FDA Guidance, 2009](#)].
- Neoplasms

Serious AESIs and elevated liver enzymes or bilirubin requiring withholding of study drug (see Section 8.4.6.1) must be reported within 24 hours of the study site personnel's knowledge of the event by marking the appropriate box on the AE eCRF and assigning the most appropriate category. Additional information should be provided as directed in the eCRF Completion Guidelines. AESIs that also meet the definition of an SAE must be reported as an SAE, as described in Section 8.4.4. Nonserious AESIs should be reported within 72 hours of the site personnel's knowledge, using the AE eCRF.

8.4.6.1. Criteria for Temporary Withholding of Study Treatment in Association with Liver Test Abnormalities

Elevated liver enzymes or bilirubin sufficient to require withholding study medication must be reported **within 24 hours of the study site personnel's knowledge of the event** using AESI specific eCRFs/forms/worksheets provided for the study.

Hepatic enzymes will be monitored in accordance with FDA drug-induced liver injury guidelines [[FDA, 2009](#)].

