If **any** of the following liver test abnormalities develop, Study Treatment should be withheld immediately with appropriate clinical follow-up (including repeat laboratory tests, until a subject's laboratory profile has returned to normal/baseline status), and the event reported as an SAE:

- ALT or AST > 8 x upper limit of normal (ULN)
- ALT or AST > 5 x ULN and persists for more than 2 weeks
- ALT or AST > 3 x ULN and total bilirubin > 2 x ULN or international normalized ratio (INR) > 1.5
- ALT or AST > 3 x ULN with appearance of fatigue, nausea, vomiting, right upper quadrant pain or tenderness, fever, rash and/or eosinophilia (> 5%)

Rechallenge may be considered if an alternative cause for the abnormal liver tests (ALT, AST, total bilirubin) is discovered and the laboratory abnormalities resolve to normal or baseline values. The investigator and Sponsor's designated Medical Monitor must discuss and agree with any decision to rechallenge.

Rechallenge should not occur when the etiology of the liver test abnormalities is considered possibly drug induced.

8.4.6.2. Criteria for Permanent Discontinuation of Study Treatment in Association with Liver Test Abnormalities

Study treatment should be discontinued permanently if **all** of the following 4 criteria are met (ie, potential severe drug-induced liver injury/Hy's law case):

- Total bilirubin increases to $> 2 \times$ ULN or INR > 1.5 **and**
- AST or ALT increases to $\geq 3 \times$ ULN **and**
- Alkaline phosphatase value does not reach $2 \times$ ULN **and**
- No alternative cause explains the combination of the above laboratory abnormalities; important alternative causes include, but are not limited to the following:
 - Hepatobiliary tract disease
 - Viral hepatitis (eg, hepatitis A/B/C/D/E, Epstein-Barr virus)
 - Exposure to hepatotoxic agents/drugs or hepatotoxins, including herbal and dietary supplements, plants, and mushrooms
 - Alcoholic hepatitis
 - Non-alcoholic steatohepatitis
 - Autoimmune hepatitis

If an alternative cause for hepatotoxicity is identified, then it should be determined (based on the severity of the hepatotoxicity or event) whether study drug should be withheld or permanently discontinued as appropriate for the safety of the subject, following consultation with the Sponsor's designated Medical Monitor.

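### Section 6.5 cites the permanent-discontinuation section for withholding drug on liver results, and Sections 7.1 and 8.4.6.2 give the same Hy's law case instructions of different force

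*Protocol*

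**What the plan says.** Four places in the protocol bear on what happens to study drug after an abnormal liver test.

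- **Section 6.5 (Dose Modification)** bars dose modification and then says "Study drug should be withheld for liver test abnormalities as described in Section" 8.4.6.2.
- **Section 7.1 (Discontinuation of Study Drug)** takes up stopping drug because of liver results and says that this "should be considered by the investigator when a subject meets all of the conditions outlined in Section 8.4.6.2". Those conditions describe a potential Hy's law case. The section also allows stopping when the investigator judges it to be in the subject's interest.
- **Section 8.4.6.1** is headed "Criteria for Temporary Withholding of Study Treatment in Association with Liver Test Abnormalities". It lists four triggers and says that if any one occurs, "Study Treatment should be withheld immediately with appropriate clinical follow-up". The event is also to be reported as an SAE.
- **Section 8.4.6.2** is headed "Criteria for Permanent Discontinuation of Study Treatment in Association with Liver Test Abnormalities". It directs permanent discontinuation when all four listed criteria are met.

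Section 8.4.6 itself uses the other pointer for withholding. Its 24-hour reporting rule covers "elevated liver enzymes or bilirubin requiring withholding of study drug (see Section 8.4.6.1". Section 7.2 adds that a subject who discontinues study drug is also withdrawn from the study.

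**The concern.** Section 6.5 is where a site would look to learn when drug is held, and its cross-reference leads to rules for a different action. The criteria found there are also much narrower: all of four conditions, against any of four.

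The second problem does not depend on the first. Section 7.1 cites 8.4.6.2 by number, so both sections address the same man, yet one calls for consideration and the other for action. Because Section 7.2 ties stopping drug to leaving the study, the choice affects his exposure, his follow-up and whether he is counted as a discontinuation due to an AE. Long-term safety is the primary objective, and a potential Hy's law case is one on which sites should not differ because of wording.

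**Working it through.** There is no planned figure to reproduce. The check sets the rules side by side and then applies them to example results.

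**1. The rules**

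| Section | Condition | Action stated |
|---|---|---|
| 6.5 | Liver abnormalities as described in 8.4.6.2 | Withhold |
| 7.1 | All the 8.4.6.2 conditions (or investigator judgement) | Consider discontinuing |
| 8.4.6.1 | Any of: ALT/AST > 8 x ULN; > 5 x ULN for more than 2 weeks; > 3 x ULN with bilirubin > 2 x ULN or INR > 1.5; > 3 x ULN with listed symptoms or eosinophilia | Withhold at once |
| 8.4.6.2 | All of: bilirubin > 2 x ULN or INR > 1.5; ALT/AST >= 3 x ULN; alkaline phosphatase (ALP) not reaching 2 x ULN; no alternative cause | Discontinue permanently |

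**2. The 6.5 pointer.** Three of the four 8.4.6.1 triggers need no change in bilirubin or INR, so none of these three satisfies 8.4.6.2 on its own. Take ALT 9 x ULN with normal bilirubin and INR. Under 8.4.6.1, 9 > 8, so the first trigger is met. Under 8.4.6.2, the bilirubin/INR criterion fails, so the set of four fails. Section 8.4.6.2 mentions withholding once, as a choice to be determined with the medical monitor when an alternative cause has been identified. It therefore does not supply the criteria that 6.5 points to.

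**3. The force of 7.1 against 8.4.6.2.** Take ALT 6 x ULN, bilirubin 2.1 x ULN, ALP 1.5 x ULN and no alternative cause. All four 8.4.6.2 criteria hold, and so does the third 8.4.6.1 trigger. The sections then state three actions: withhold (6.5 and 8.4.6.1), consider stopping (7.1) and stop permanently (8.4.6.2).

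**4. An illustrative grid.** The two rules in 8.4.6 were applied to ALT/AST of 2.9, 3.0, 3.1, 6 and 9 x ULN; bilirubin of 1.5, 2.0 and 2.1 x ULN; INR of 1.0 and 1.6; ALP of 1.5 and 2.0 x ULN; and alternative cause yes or no. That gives 5 x 3 x 2 x 2 x 2 = 120 combinations. Elevations were taken as asymptomatic and not persistent, and the third trigger was read as ALT/AST > 3 x ULN together with either raised bilirubin or raised INR.

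- Raised bilirubin or INR holds in 4 of the 6 bilirubin-by-INR pairs, which is 4 x 4 = 16 of the 24 cells at each ALT/AST level.
- Withholding rule met: 16 (at 3.1) + 16 (at 6) + 24 (at 9) = 56.
- Permanent rule met: 4 at each of 3.0, 3.1, 6 and 9 = 16.
- Both met: 12. Withholding only: 56 - 12 = 44. Permanent only: 16 - 12 = 4, all at exactly 3.0 x ULN.

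These counts depend on the values chosen and are not event rates. They show that the two sections are not interchangeable as targets for 6.5. The four permanent-only cells come from the > 3 against >= 3 mismatch.

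**The case against.** The strongest reply is that Section 8.4.6 works without Section 6.5. Section 8.4.6.1 requires immediate withholding on its own terms, and it directly precedes the section that 6.5 cites. Sections 8 and 8.3 also send immediate safety concerns to the medical monitor. This stands, and it limits the first part of the point. A reader might infer that a man with ALT 9 x ULN stays on drug under 6.5. The text does not say so: 6.5 contains no instruction to continue, and a site that kept dosing would breach 8.4.6.1.

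A reader might also infer that only sites using 8.4.6.1 would generate the adverse event of special interest and the 24-hour report. The documents do not support that either. The special-interest definition cites both 8.4.6.1 and 8.4.6.2, and the 24-hour rule cites 8.4.6.1 and is repeated at its head.

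Nor do 8.4.6.1 and 8.4.6.2 clearly conflict with each other. They can largely be read as steps: hold at once, then stop permanently if ALP and the search for other causes confirm the case. At exactly 3 x ULN the permanent rule already stops drug, so no man receives opposing orders there.

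Exposure to the problem is limited. Scheduled laboratory tests within this study fall at Weeks 36 and 52, and no drug is supplied after Week 52. The results that could change dosing are therefore essentially Week 36, Week 24 results returned after entry, and unscheduled tests. Section 8.4.6 reports no liver-toxicity concern to date, and SAP Section 7.4 examines liver values directly, whatever dosing decision was taken.

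None of this removes the wrong pointer or reconciles 7.1 with 8.4.6.2. Section 7.1 does send its reader to the stronger wording, but that leaves the site with two instructions for one case.

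**Conclusion.** The point holds as an internal inconsistency that should be fixed. It has two substantive parts: the 6.5 cross-reference does not lead to the withholding criteria, and 7.1 and 8.4.6.2 give different force to the same stopping rule. The threshold mismatch at 3 x ULN is minor.

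The second part matters more, because the stepwise reading of 8.4.6 does not resolve it and Section 7.2 turns the choice into study withdrawal. The documents give no expected rate of such cases. With about 300 men, each case handled differently moves the discontinuation proportion by 1/300, or about 0.3 percentage points. The descriptive summaries would barely change; the importance lies in the individual case. The conclusion rests on the protocol wording alone, not on any assumption about vibegron's liver safety, and takes no position on which clinical rule is right.

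**What to change.** Reconcile Sections 6.5, 7.1, 8.4.6.1 and 8.4.6.2 so that a given liver result leads to one stated action:

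- make the 6.5 cross-reference agree with the section that holds the withholding criteria;
- give 7.1 and 8.4.6.2 the same force for a subject who meets all the 8.4.6.2 conditions;
- use one inequality at 3 x ULN in both 8.4.6.1 and 8.4.6.2.

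The sponsor and its medical monitor decide the clinical content of each. The cost is protocol wording, one cross-reference and a short note to sites. No assessments are added.

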6.6. Drug After the End of the Study

Study drug (vibegron) will not be provided after the Week 52 visit.

7. Discontinuation of Study Drug and Subject Discontinuation or Withdrawal

A premature discontinuation will occur if a subject who signs the informed consent form (ICF) and is dosed ceases participation in the study, regardless of circumstances, before the completion of the protocol-defined study procedures.

7.1. Discontinuation of Study Drug

Subjects who discontinue study drug will complete the Week 52/Early Withdrawal assessments specified in the Schedule of Assessments (Section 1.3).

Reasons for discontinuation from the study drug include the following:

- Any AE of urinary retention
- Any occurrence of PVR volume \geq 300 mL

Discontinuation of study drug for abnormal liver function should be considered by the investigator when a subject meets all of the conditions outlined in Section 8.4.6.2 for Hy's law or if the investigator believes that it is in best interest of the subject (reason for discontinuation will be AE).

7.2. Subject Discontinuation/Withdrawal from the Study

- A subject who discontinues study drug will also be withdrawn from the study.
- A subject may choose to withdraw from the study at any time at his own request, or may be withdrawn at any time at the discretion of the investigator for safety, behavioral, compliance, or administrative reasons.
- If a subject withdraws consent for disclosure of future information, the Sponsor or designee may retain and continue to use any data collected before such a withdrawal of consent.
- If a subject withdraws from the study, he may request destruction of any blood or urine samples taken and not tested, and the investigator must document this in the site study records.
- Subjects who withdraw from the study will not be replaced.

The Week 52/Early Withdrawal assessments will be completed when a subject withdraws or is withdrawn from the study, if possible (see Schedule of Assessments in Section 1.3).

Reasons for discontinuation from the study include the following:

- AE
- Lack of efficacy
- Noncompliance
- Withdrawal of consent
- Lost to follow-up
- Physician decision
- Protocol deviation
- Death
- Other

7.3. Lost to Follow Up

Should a subject fail to attend a required study visit, the site should attempt to contact the subject and re-schedule the missed visit as soon as possible. The site should also counsel the subject on the importance of maintaining the assigned visit schedule and ascertain whether or not the subject wishes to and/or should continue in the study based on previous non-compliance. In cases where the subject does not return for the rescheduled visit or cannot be reached to reschedule the missed visit, the site should make every effort to regain contact with the subject so that they can appropriately be withdrawn from the study with a primary reason of “Lost to Follow-up”. Including at least three documented attempts to contact the subject (ie, phone, email, or certified letter). Efforts to establish the possible reason for discontinuation should be documented.

7.4. Early Study Termination

The Sponsor reserves the right to terminate the study for any reason. The study may be terminated early if the extent (incidence and/or severity) of emerging effects/clinical endpoints is such that the risk/benefit ratio to the study population as a whole is unacceptable. In addition, further recruitment in the study overall or at a particular study site may be stopped due to insufficient compliance with the protocol, Good Clinical Practice and/or other applicable regulatory requirements, procedure-related problems or the number of discontinuations for administrative reasons is too high.

8. Study Assessments and Procedures

Study procedures and their scheduled timepoints are summarized in the Schedule of Assessments (Section 1.3). A detailed listing of study assessments by visit is provided in Section 10.7. Site personnel should note the following:

- Protocol waivers or exemptions are not allowed. Any notable protocol deviations should be noted and raised to the Sponsor's or designee's attention.
- Immediate safety concerns should be discussed with the Sponsor's designated Medical Monitor immediately upon occurrence or awareness to determine if the subject should continue or discontinue study drug.
- Adherence to the study design requirements, including those specified in the Schedule of Assessments, is essential and required for study conduct.
- Note that patient-reported outcome (PRO) assessments will be completed prior to vital signs, and vital signs will be taken prior to blood draws.
- Procedures conducted as part of the subject's routine clinical management (eg, blood count) and obtained before signing of the ICF may be utilized for the purposes of confirming eligibility (in addition to the most recent available assessments from Study URO-901-3005).

8.1. Study Entry Procedures

As this is an extension study that includes subjects from the ongoing parent study, URO-9013005, assessments performed at the end of the parent study will not be repeated on study entry into Study URO-901-3006. Specifically, vital sign, physical examination, laboratory, bladder diary, PVR urine, and PRO assessments performed at the Week 24 Visit of Study URO-901-3005 will be considered the initial study assessments at entry into extension Study URO-901-3006.

In addition, medical history and demographic information from entry into Study URO-901-3005 will be used as relevant to provide information for Study URO-901-3006.

8.1.1. Informed Consent

Documented consent (for Study URO-901-3006) must be obtained from each potential subject prior to the first dose of open-label study drug (vibegron) on Study URO-901-3006 according to the process described in Section 10.1.3.

8.1.2. Assignment of Subject Number

All subjects who enroll in Study URO-901-3006 will retain the same study number that they were assigned in Study URO-901-3005.

The investigator will maintain a log to confirm eligibility or record reasons for ineligibility, as applicable. Inclusion and exclusion criteria (Section 5.1 and Section 5.2) will be reviewed by the investigator or qualified designee at Week 24 of Study URO-901-3005. If needed, the Week 24 laboratory results from Study URO-901-3005 may be used to confirm eligibility.

8.1.3. Concomitant Medications

Ongoing medications will be recorded beginning at the signing of the ICF and continuing until the last dose of study drug.

8.2. Efficacy Assessments

Efficacy assessments will be collected as outlined in the Schedule of Assessments (Section 1.3) in the form of 3-day Bladder Diary. Information collected in the diaries will be used for assessment of the efficacy endpoints related to the number of micturition, urgency, nocturia, and incontinence episodes per day as well as the volume voided per micturition. In addition, subjects will complete IPSS assessments and [REDACTED] Patient Global Impression (PGI), and [REDACTED] scores to assess quality of life parameters.

Subjects will complete questionnaires at the site at the start of each required study visit (before vital signs and blood draws). The PRO questionnaires are provided in Section 10.8. Additional information on the Bladder Diary and questionnaires is provided below.

8.2.1. Bladder Diaries

Bladder Diary is used by subjects to record the frequency of daily OAB symptoms including all micturitions, urgency, incontinence, nocturia, one 24-hr volume voided of urine (used to derive the volume per micturition), and main reason for incontinence, and volume voided per micturition (over one 24-hour period) by selecting the respective box for each symptom occurring during the course of a given day and night.

The Bladder Diary should be completed by the subject on 3 consecutive days within the 7 days prior to Visit 12 (Week 28), Visit 13 (Week 36) and Visit 14 (Week 52). A “Diary Day” is defined as the time between when the subject gets up for the day each morning (ie, the time the subject got up for the day yesterday to the time the subject got up for the day today; approximately a 24-hour period). Urine volume may be collected during any one (1) of the 3 Diary Days prior to the visit.

At all study visits, the site staff should inquire whether the subject had any difficulties with the diary and address any questions subjects may have. Instructions for proper completion of the diary should be re-reviewed. Subjects will be trained to enter data immediately following each event (in real time) and to input data from any “missed” events as soon as they are able. They will review and confirm that data from all events occurring within the preceding Diary Day (approximately 24 hours) have been entered at a consistent time each morning (eg, upon getting up for the day).

8.2.2. Patient-Reported Outcomes

Subjects will complete questionnaires at the site at the start of each required study visit (before vital signs and blood draws) to assess subject-perceived symptom relief, symptom bother, and health-related quality of life. These include the following questionnaires:

- The IPSS includes 8 questions (7 concerning urinary symptoms and 1 concerning quality of life), each with answers based on a 6-point scale indicating increasing severity. The urinary symptom responses are assigned points from 0 to 5. The Total IPSS Score can therefore range from 0 to 35 (asymptomatic to very symptomatic). The quality of life responses are assigned points from 0 to 6. A sample of the IPSS is provided in Section 10.8.1.
- [REDACTED] (1-week recall) is a multi-item questionnaire that was developed to assess symptom bother and the impact of [REDACTED]. The instrument was developed and validated in both continent and incontinent OAB patients, including both men and women. A sample of the [REDACTED] scales is provided in Section 10.8.2.
- The EQ-5D health questionnaire is a standardized instrument for use as a measure of health outcome [Rabin 2014]. It is applicable to a wide range of health conditions and treatments; it provides a simple descriptive profile and a single index value for health status. A sample of the EQ-5D health questionnaire is provided in Section 10.8.3.
- Global Impression Items include [REDACTED]. [REDACTED] A sample of the PGI scale is provided in Section 10.8.4.
- [REDACTED]

The investigator should not provide any additional information to subjects prior to completing the questionnaires that might influence responses.

